Each pill bottle of study drug will be labeled with the required FDA warning statement, the protocol number, a treatment number, the name of the study physician, and directions for patient use and storage.

Administration of Study Drug

Dosage/Dosage Regimen

If subjects meet inclusion criteria, they will be seen both in the hospital and at IDAS clinic for a total of 12 active study days and monitoring procedures will be in place to detect drug and alcohol use and assess for adverse events at each visit. In addition, the hospital cocaine administration procedures will reduce the likelihood of increased cocaine craving after cocaine administration. Subjects will undergo procedures as described below. Subjects will not be allowed to smoke cigarettes, as smoking is not allowed in the hospital or anywhere on the VCU campus. Subjects will have the option to use a nicotine patch dosed based on the amount of daily cigarettes smoked. Subjects will not be allowed to leave the CRS Unit nor receive visitors during their study visits. Subjects who are unable to comply with these restrictions will be dropped from the study. After a screening cocaine infusion to determine safety, eligible subjects will be randomized to Group A –placebo only or Group B –placebo followed by an ascending dose of lorcaserin. Six subjects will be assigned to Group A (placebo) and 12 subjects will be assigned to Group B (active lorcaserin).

Study Drug Dosage: Lorcaserin will be 10mg once daily increasing to 10mg twice daily.

Outcome Measures: The primary outcome measures are adverse events, cardiovascular responses (Heart rate (HR), blood pressure (BP), ECG measurements, subjective response to cocaine, cocaine self-administration, and cocaine blood PK. Secondary outcome measures will be impulsivity as measured by the immediate memory task (IMT).

- 1) Days 1-2: All subjects will be seen on the CRSU. All subjects will receive placebo on days 1-2 in a single blind fashion. Vital signs including heart rate, blood pressure and respiration rate will be obtained after placebo administration. Days 1-2 will be single-blind placebo, whereas all remaining study days will be double-blind. All subjects will leave the CRSU at the end of each study day.

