In this task, the subject sees the letters X and Y alternating once per second (white letter on black background) in a large font, e.g. 400 ms of letter presentation, alternating with 600 ms blank screen. The subject is to emit a press each time the letter is different from the one before (an alternation). Since most of the time X alternates with Y, this builds up a prepotent tendency of the subject to press every second. However, the subject is to NOT press if the same letter is presented twice in a row, e.g. ..X....Y.....X....X..... or X....Y.....X....Y....X....Y....Y... The presentation of the same letter twice in a row in the series is called a LURE, and these represent 10% of the stimuli, and lures never occur in rapid succession. The task will be divided into 15 blocks, each 30 seconds long. Each block will thus have 30 letters shown, three of which will be identical to the letter before it (i.e. three lures per block. Five blocks will be "non-distractor" control blocks, where the background will be black as in the original Garavan task. Five blocks will be "unconditioned distractor) control blocks, where the subject will see a continuous thick yellow border at the periphery of the screen. Five blocks will be the "conditioned distractor" blocks, where the subject will see a continuous teal-colored thick border that was previously seen in the cocaine self-administration task.

Adverse Events

Information regarding occurrence of adverse events will be captured throughout the study. Duration (start and stop dates and times), severity, outcome, treatment and relation to study drug will be recorded on the case report form (CRF).

Clinical Laboratory Measurements

Hematology

Blood will be obtained and sent to each site's clinical hematology lab a complete blood count (hemoglobin, hematocrit, red blood cell count, white blood cell count, white blood cell differential, and platelet count).

Blood Chemistry Profile

Blood will be obtained and sent to each site's clinical chemistry lab for determination of serum sodium, potassium, chloride, bicarbonate, random glucose, BUN, creatinine, aspartate aminotransferase (AST/SGOT), alanine aminotransferase (ALT/SGPT), alkaline phosphatase, total bilirubin, direct bilirubin, albumin and LDH.

Pregnancy Test

A urine pregnancy test will be obtained from female subjects who are of childbearing age prior to their participation in the study.

Urinalysis

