Update concomitant medications.

Administer cocaine for PK.

Measure lorcaserin PK.

Conduct clinical assessments (POMS, CGI-I).

Administer cocaine for Dosing session 4.

Administer IMT task

Administer placebo/lorcaserin in evening
Leave CRS unit.

Study Day 11

Arrive on CRS unit
Administer placebo/lorcaserin in morning
Collect urine for pregnancy test and urine drug screen.
Collect blood for clinical laboratory tests (serum chemistry and hematology).
Perform and record Breathalyzer and vital signs.
Perform a 12-Lead ECG and continuous cardiovascular monitoring.
Record brief substance craving scale, VAS and AE.
Administer COWS if opioid user.
Update concomitant medication.
Self -Administered cocaine session 5 in morning.
Self -Administered cocaine session 6 in afternoon.
Conduct clinical assessments (POMS, CGI-I).
Leave CRS unit.

Study Day 12

Arrive at IDAS
Collect urine for pregnancy test and urine drug screen.
Perform and record Breathalyzer and vital signs.
Perform a 12-Lead ECG.
Record brief substance craving scale and AE.
Administer COWS if opioid user.
Update concomitant medication.
Conduct clinical assessments (POMS, CGI-I, Stroop, and XY Go-No Go).
PI (or designee) conduct assessment for lorcaserin side effects.
Leave IDAS

Follow-Up Days (Day 15, 19) Conducted at IDAS

Collect urine for pregnancy test and urine drug screen.
Perform and record Breathalyzer and vital signs.
Perform a 12-Lead ECG and brief physical exam (Day 19 only).
Record brief substance craving scale and timeline follow back cocaine use.
Update concomitant medication.
Conduct clinical assessments (POMS, CGI-I, and C-SSRS).

Table 2. Overview of Study Procedures

Study Day	Day 1	Day 2
Study Visit	One	Two
Procedure Morning Session	Arrive at CRS, Three Screening Doses of Cocaine (NexFin monitoring)	Arrive at CRS 10mg Cocaine for PK
Procedure Afternoon Session	Impulsivity Testing Depart from CRS	Three Doses of Cocaine, Cardiovascular (NexFin monitoring) Cardiac Biomarkers (4-6 hrs from last dose) Subjective Ratings Depart from CRS
Study Drug	Placebo 8:00 a.m.	Placebo 8:00 a.m

Study Day	Day 3	Day 4	Day 5	Day 6	Day 7
Study Visit	Three	Four	Five	Six	Seven Arrive at CRS ECG
Procedure Morning Session	Arrive at CRS Cocaine Self Administration	Arrive at IDAS ECG Impulsivity Testing	Arrive at IDAS ECG	Arrive at CRS ECG 10mg Cocaine for PK, Lorcaserin blood levels	Cocaine Self Administration

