Possibly	An event that follows a reasonable temporal sequence from administration of the drug; that follows a known or expected response pattern to that suspected drug; but that could readily have been produced by a number of other factors.
Unrelated	An event that can be determined with certainty to have no relationship to the study drug.

Serious Adverse Experiences (SAE)

An SAE is defined as any AE occurring at any dose that results in any of the following outcomes:

- death
- a life-threatening adverse experience
- inpatient hospitalization or prolongation of existing hospitalization
- a persistent or significant disability/incapacity
- a congenital anomaly/birth defect

Other important medical events may also be considered an SAE when, based on appropriate medical judgment, they jeopardize the subject or require intervention to prevent one of the outcomes listed.

Serious Adverse Experience Reporting

All adverse events (AEs) occurring during the course of the study will be collected, documented, and reported to the PI. The occurrence of AEs will be assessed at baseline and each clinic visit during the treatment phase of the study.

AE's deemed to be serious (SAEs), as defined by the FDA, will be systematically evaluated at each clinic visit. Any SAE, whether or not related to study, will be reported to the VCU IRB, the NIDA Program Officer ([name], and the FDA (when appropriate) within 24-48 hours. A full written report to all institutions will follow as soon as possible but in no more than three days. The written report will be in the format required by the local IRB and will contain information regarding the date of the SAE, description of the SAE, severity rating (Grade 1 to 4), assessment of cause, whether the SAE indicates an increased risk for current or future subjects, and whether changes to the informed consent form will be necessary.

In cases of early termination from the study due to SAE, the participant will have appropriate follow-up medical monitoring. Monitoring will continue until the problem has resolved or stabilized with no further change expected, is clearly unrelated to study medication, or results in death. Outcome of SAEs will be periodically reported to NIDA. A summary of the SAEs that occurred during the previous year will be included in the annual progress report to NIDA.

Medical Monitoring

Dr. [name] should be contacted directly at these numbers to report medical concerns or questions regarding safety.

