Children as defined by NIH (age 18-21 years) will be included in this research. The incidence of severe cocaine abuse/dependence is relatively small in the population of youth less than 18 years old. From a safety perspective, risks of exposure to the proposed study medication and cocaine administration in substance-dependent children under 18 have not been established.

Analysis of Primary Endpoint

1. Safety: Heart rate (HR) and blood pressure (BP) measures during saline infusions will be compared to HR and BP after each cocaine infusion (20 mg and 40 mg doses). Changes in HR and BP induced by cocaine infusion along with lorcaserin will be compared to those without lorcaserin, by cocaine dose level (20 mg and 40 mg doses), using repeated measures analysis of variance (ANOVA). Changes in ECG readings during saline infusion as compared to those taken during cocaine infusions will be reported as summary statistics. Adverse event data will be compiled for lorcaserin and placebo cohorts and presented as summary statistics.
2. Cocaine Self-administration: Repeated measures ANOVA with cocaine dose (0mg, 25mg) and lorcaserin dose (0mg, 10mg, 20mg) as within subject factors will be used to examine differences in mean cocaine choice selection. In addition, a Bayesian analysis will be carried out as described below.
3. Subjective response to cocaine: Subjective response measures (VAS) obtained during saline infusions will be compared between lorcaserin and placebo subjects to those during cocaine infusions by cocaine dose level to determine the extent to which these measures are modified by the administration of lorcaserin using repeated measures ANOVA.
4. Cocaine PK: Plasma concentration-time profiles of cocaine after cocaine infusion during placebo administration (Day 2) will be analyzed to obtain pharmacokinetic parameter estimates of cocaine (Tmax, AUC, apparent t_{1/2}, CL) by individual. These parameters will be compared within subjects on sessions with lorcaserin (Day 6 and 10).

Analysis of Secondary Endpoints

Response inhibition: Commission errors on the IMT will be compared between lorcaserin and placebo subjects to determine the extent to which this measure is modified by the administration of lorcaserin using repeated measures ANOVA.

Safety and tolerability data will be summarized by treatment group.

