Adverse event rates will be coded by body system and MedDra classification term. Adverse events will be tabulated by treatment group and will include the number of patients for whom the event occurred, the rate of occurrence, and the severity and relationship to study drug.

Interim Analysis

When approximately 50% of patients have completed the study, an interim analysis for safety will be conducted by the DSMB. Serious adverse events will be monitored by the committee on an ongoing basis throughout the study.

Sample Size and Randomization

This project requires a final sample size of 18 subjects (Six subjects assigned to Group A (placebo) and 12 subjects assigned to Group B (active lorcaserin)). This sample size for effect of lorcaserin on cocaine self-administration was based on previous research showing effects of medication on human cocaine self-administration (Hart et al, 2008). In an effort to increase the power of the study, a Bayesian approach will also be utilized that incorporates information from previous studies. This approach will use a Bayesian hierarchical model with subject at the lowest level of the hierarchy and treatment group at the second level. This model is analogous to the repeated measures ANOVA except that prior information will be introduced. Since many similar studies have been conducted with cocaine users and the same outcome measures we will assign an

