APPENDIX 1. DETAILED TIMELINE OF MEASURES

Procedure	Screening Day	Study Day												Follow-up	
	-90 to 0	1	2	3	4	5	6	7	8	9	10	11	12	15, 19	
Informed Consent	X														
Serum Chemistry	X											X			
Hematology	X											X			
History, Physical Exam, and Neurological Exam	X	X	X									X			
Urine Pregnancy test (females)	X	X	X	X	X	X	X	X	X	X	X	X	X	X	X
Psychiatric Interview (SCID)	X														
Kreek-McHugh-Schluger-Kellogg scale (KMSK)	X														
Fagerstrom Test for Nicotine Dependence (FTND)	X														
National Adult Reading Test (NART)	X														
Addiction Severity Index (ASI-lite)	X														

Brief Substance Craving Scale	X	X	X	X	X	X	X	X	X	X	X	X	X	X
Timeline Follow Back Cocaine Use	X													X
Drug Use History	X													
Concomitant Medications	X	X	X	X	X	X	X	X	X	X	X	X	X	X
Clinical Opiate Withdrawal Scale (COWS)	X	X	X	X	X	X	X	X	X	X	X	X	X	
Urine drug screen	X	X	X	X	X	X	X	X	X	X	X	X	X	X
Breathalyzer	X	X	X	X	X	X	X	X	X	X	X	X	X	X
Verify Inclusion & Exclusion	X	X	X											
Vital Signs	X	X	X	X	X	X	X	X	X	X	X	X	X	X
12-Lead ECG (baseline triplicate) and singlet thereafter)	X	X	X	X	X	X	X	X	X	X	X	X	X	X
Continuous Cardiovascular Monitoring		X	X	X			X			X			X	
Brief Physical Exam		X	X	X					X				X	X (Day 19 only)
Cocaine Administration for 3 Doses		X	X				X				X			

Adverse Events Inventory		X	X	X	X	X	X	X	X	X	X	X	X	
Visual Analog Scale (VAS)		X	X	X			X	X			X	X		
Profile of Mood States (POMS)	X	X	X	X	X	X	X	X	X	X	X	X	X	X
Clinical Global Impression Severity & Improvement (CGI-S&I) (baseline CGI-S, and CGI-I thereafter)	X	X	X	X	X	X	X	X	X	X	X	X	X	X
Columbia Suicide Severity Rating Scale (C-SSRS) (Lifetime version at screening and since last visit version thereafter)	X	X				X			X					X
Cocaine for PK			X				X				X			
Lorcaserin PK measurement							X				X			
Cardiac biomarkers (baseline and 4-6 hours after last dose)			X				X				X			

Lorcaserin or Placebo		X	X	X	X	X	X	X	X	X	X			
Cocaine Self-administration				X				X				X		
Immediate Memory Task (IMT)		X			X			X			X			
Stroop													X	
XY Go-NoGo													X

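### Adverse-event tables by arm define no treatment-emergent window, and the documents contradict themselves on recording adverse events at the Day 15 and Day 19 follow-up visits

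*Combined protocol and SAP*

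**What the plan says.** **Tabulation.** Analysis of Primary Endpoint, item 1, says: "Adverse event data will be compiled for lorcaserin and placebo cohorts and presented as summary statistics". Analysis of Secondary Endpoints adds: "Adverse events will be tabulated by treatment group and will include the number of patients for whom the event occurred", together with rate, severity and relationship to study drug. Neither section gives a start date, a treatment-emergent rule, or a split by period or dose. AEs are named among the primary outcome measures in Dosage/Dosage Regimen.

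**Exposure.** The same section says: "All subjects will receive placebo on days 1-2 in a single blind fashion". On Days 3 to 6, Group B takes placebo in the morning and its lorcaserin capsule in the evening. The Study Day 3 list puts both cocaine self-administration sessions before that evening capsule. The last lorcaserin dose is on the morning of Day 11.

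**Capture.** The Adverse Events paragraph in Study Procedures and Guidelines says: "Information regarding occurrence of adverse events will be captured throughout the study". Serious Adverse Experience Reporting says: "The occurrence of AEs will be assessed at baseline and each clinic visit during the treatment phase of the study". The list headed "Follow-Up Days (Day 15, 19) Conducted at IDAS" has no AE item. In Appendix 1 the row "Adverse Events Inventory" is marked for Days 1 to 12, and its follow-up column is blank.

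**The concern.** This is the first human use of the combination, according to the protocol's own risk section, and the results are meant to inform go/no-go decisions. A safety summary that mixes pre-exposure time into the active arm makes the two arms look more alike than they are. For safety that is the unfavourable direction.

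The other primary outcomes do separate exposure. Day 2 is the placebo reference for cocaine PK. Self-administration uses lorcaserin 0, 10 and 20 mg as a factor. Heart rate and blood pressure are compared with and without lorcaserin. So a Group B subject's Day 3 sessions are 0 mg data for self-administration, while an AE in those same sessions would be tabulated under lorcaserin.

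At the other end, staff who work from the visit list or Appendix 1 would not be prompted to ask about AEs on Days 15 and 19. No later analysis can recover an event that nobody asked about.

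**Working it through.** The plan states no figure on this point, so there is none to reproduce. The check is a day count, an illustration of dilution, and a comparison of passages.

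**1. Day count** (Dosage/Dosage Regimen, the visit lists, Table 2, Appendix 1)

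- Days with cocaine: 1, 2, 3, 6, 7, 10, 11, which is 7 days.
- Cocaine days completed before the first lorcaserin capsule: 1, 2, 3, so 3/7 = 43%.
- Days with a scheduled AE inventory: 1 to 12. Of these, Days 1, 2 and 3 (until evening) precede lorcaserin, so 3/12 = 25%. Counting only days wholly free of lorcaserin gives 2/12 = 17%.
- Randomization: "After a screening cocaine infusion to determine safety, eligible subjects will be randomized". Table 2 labels the Day 1 infusions as screening doses, so some Day 1 events may even precede allocation.
- Study days need not be consecutive, provided all fall within 90 days. Days 1 and 2 may be scheduled well ahead of Day 3, so the pre-dose interval can be longer in calendar time than the day numbers suggest.

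**2. Dilution, on the patient-count scale that the plan uses**

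Let q be the probability of at least one AE before the Day 3 evening dose. It is the same in both arms because treatment up to then is the same. Let p0 and p1 be the post-dose risks on placebo and lorcaserin, taken as independent of pre-dose events. Then:

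- whole-window risk in an arm = 1 − (1 − q)(1 − p)
- whole-window risk difference = (1 − q)(p1 − p0)

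The documents give no AE rates. Assumed: p0 = 0.20, p1 = 0.50.

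| q | Placebo | Lorcaserin | Difference | Ratio | Expected patients, 6 vs 12 |
|---|---|---|---|---|---|
| 0 (post-dose events only) | 0.20 | 0.50 | 0.30 | 2.50 | 1.2 vs 6.0 |
| 0.2 | 0.36 | 0.60 | 0.24 | 1.67 | 2.2 vs 7.2 |
| 0.4 | 0.52 | 0.70 | 0.18 | 1.35 | 3.1 vs 8.4 |
| 0.6 | 0.68 | 0.80 | 0.12 | 1.18 | 4.1 vs 9.6 |

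Example at q = 0.4: placebo 1 − 0.6 × 0.8 = 0.52; lorcaserin 1 − 0.6 × 0.5 = 0.70; difference 0.18 = 0.6 × 0.30.

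The factor (1 − q) does not depend on the assumed post-dose risks. With 20% and 40% instead, the difference of 0.20 becomes 0.16 at q = 0.2 and 0.12 at q = 0.4.

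**3. AE capture at follow-up: the passages side by side**

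| Requires or implies capture on Days 15 and 19 | Omits it |
|---|---|
| Adverse Events, in Study Procedures and Guidelines: whole study | Follow-Up Days visit list: no AE item |
| Adverse Events, in Adverse Experience Reporting and Documentation: recorded at any visit | Appendix 1: AE row marked Days 1 to 12 only |
| Serious Adverse Experience Reporting, first sentence: every AE during the study | Same section, next sentence: baseline and treatment-phase visits |

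If days run consecutively, the last scheduled AE inventory is 1 day after the last lorcaserin dose (Day 12 against Day 11). The two visits without one fall 4 and 8 days after it.

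**The case against.** **The plan does not say that pre-dose events go into the lorcaserin column.** Correct. That follows from the absence of any window, combined with an inventory that starts on Day 1. A detailed SAP is promised and could supply the definition, and start and stop dates and times are recorded, so no new data are needed. This stands as a reason why the repair is easy. It does not remove the gap: the SAP is due only before analysis of the final data, whereas the safety interim analysis comes at about 50% completion.

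**Relationship to study drug is tabulated, and Days 1 and 2 are single-blind placebo.** Staff could therefore rate those events as unrelated to lorcaserin. This helps in part. It does not cover Day 3, which is double-blind, and the events would still be counted in the arm totals.

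**Dilution cannot reverse a decision.** AEs are only summarised, for 6 versus 12 subjects, with no test or decision rule, and both arms share the same pre-dose period. This stands and limits the consequence to a blurred descriptive comparison.

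**A reader might infer that AE capture ends on Day 12.** The documents do not support that as a rule: three statements require wider capture, SAEs are to be evaluated at each clinic visit, and Day 12 itself comes after the last dose. What they show is a contradiction.

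**A reader might also scale the dilution by cocaine days**, turning a doubled event rate into (3 + 4 × 2)/7 = 1.57. That assumes equal event rates on every cocaine day and one constant effect at both doses. It describes event rates, whereas the quoted table counts patients.

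**Conclusion.** The concern holds in two limited parts.

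First, with no treatment-emergent window, the arm-level AE tables as written pool placebo-only time, from Day 1 to the Day 3 evening capsule, with lorcaserin time. That interval contains three of the seven cocaine days. The effect is dilution toward no difference, by the factor (1 − q) for patient counts. The sizes shown rest on assumed risks, on equal q in the two arms and on independence of pre- and post-dose events. They illustrate the mechanism and do not forecast this trial.

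Second, the documents are inconsistent about AE recording on Days 15 and 19. If the visit list and Appendix 1 are followed, non-serious events arising after Day 12 may go unasked and be lost.

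The point is worth correcting because AEs are a primary outcome and the correction is nearly free. It does not invalidate the safety assessment.

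**What to change.** 1. **Window.** In the statistical section now, and in the SAP, base the lorcaserin–placebo AE summary on events that start or worsen after the Day 3 evening dose, in both arms, using the onset dates and times already recorded. List pre-dose events separately. Use the same rule for the DSMB's safety interim analysis.
2. **Periods.** Show the once-daily, twice-daily and post-treatment periods descriptively only, and state where Day 7 (no lorcaserin capsule) and any gap between visit blocks belong. Dose order is fixed and so confounded with time and repeated cocaine exposure, and cells are small. These displays should carry no by-dose inference.
3. **Capture.** Add the AE inventory to Days 15 and 19 in the Follow-Up Days list and in Appendix 1. Align the treatment-phase sentence in Serious Adverse Experience Reporting with the two Adverse Events paragraphs.

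Cost: one form at two visits that already take place, short wording changes in the protocol and SAP, and a little more tabulation. No dose or clinical procedure changes.
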